### 7.3.4 Interim Analysis

No interim analysis is planned during this trial.

### 7.3.5 Safety Analysis

No safety analysis is necessary as the procedures performed are within the scope of practice of the researchers and utilize publicly available equipment.

### 7.3.6 Deviation(s) from the original statistical plan

Deviations to the statistical plan will be captured and reported in an update to this document, with justification.

## 7.4 Handling of missing data and drop-outs

Participants with missing procedure time data for either or both methodologies will be excluded from statistical analysis entirely. Missing qualitative data will not impact statistical analysis (as no statistical analysis is planned for qualitative data). Drop-outs will not be replaced during this study. Achieved statistical power will be calculated and documented if the planned sample size is not achieved.

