### 5 Objectives and hypotheses of the clinical investigation

#### 5.1 Purpose of the clinical investigation claims for clinical performance, effectiveness or safety of the investigational device that are to be verified

The purpose of this study is to better understand the value drivers behind the [REDACTED]. The study intends to find any significant difference in the time it takes to complete the workflow of the [REDACTED] 3D ear scanner impressions, compared to a traditional silicone earmold impression (EMI). A secondary purpose of this study is to identify preferences between the [REDACTED] and traditional methods, for both patients and providers. This information will allow us to find out whether this is a viable piece of equipment for Audiological Care clinics.

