## Clinical Investigation Plan (CIP)

Expected duration of each participant's participation	Approximately 30 minutes
Number of participants required to be included in the clinical investigation, and where needed anticipated distribution of enrolment among the participating clinical sites.	30 subjects seen at PARC
Estimated time needed to select this number (i.e. enrolment period).	Approximately 2 weeks
Relationship of investigation population to target population	Investigation population will contain a variety of external auditory canal sizes and shapes, relatable to the average patient without any external auditory canal anomalies.
Information on vulnerable, pregnant and breastfeeding population, if applicable.	N/A

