### 6.4 Procedures

#### 6.4.1 Investigation-related Procedure

Three researchers will be facilitating these appointments to limit variability of researcher skill across the two conditions. Researchers will familiarize themselves with the [REDACTED] equipment through independent practice prior to a training facilitated by [REDACTED] (occurring April 23rd) and the researchers will follow [REDACTED] training recommendations (perform scans on 20+ ears following in-person training) prior to data collection. Participants will be seen for one appointment. REUR/REUG, RECD, tympanometry, and reflex thresholds will be collected. The researcher will perform both traditional earmold impressions and 3D ear scans on both ears (conditions will be randomized and counterbalanced across participants). An additional researcher will use a stop watch to quantify the time (mm:ss) it takes for each condition, for both ears. After each procedure, participants and the clinician will also be asked to complete a questionnaire regarding each condition, focusing on their perception of comfort and level of involvement throughout the impression taking. In the event that a clinician feels as though a silicone impression needs to be remade, this will be recorded on the clinician questionnaire. Timing will be recorded for all attempts, but only the time recorded for the final impressions will be used in the data analysis. The resulting data will be compiled for all participants and analyzed using a T-test, to identify any significant differences in the time it takes to complete each method of earmold impressions, in addition to any differences in perceptual comfort.

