## Clinical Investigation Plan (CIP)

- Introduction – “I will be taking some impressions of your ear canals. I will place this foam block in each ear, before filling your canals with the silicone impression material. It will take a few minutes to harden before I remove them. Due to the nature of this study, I am going to ask you to hold any questions until after the procedure is done, but do not hesitate to let me know if you are experiencing any discomfort throughout the procedure.”
- Have materials out and ready to go (impression cartridge in impression gun, box folded together, but do not put a tip on the impression gun)
- Otoscopy
- Cerumen management if needed
- Start timer
- Tie off otoblocks
- Place otoblocks bilaterally
- Confirm otoblock placement with otoscopy
- Put tip on impression gun
- Administer impression material bilaterally
- Check hardness of silicone every 30 seconds
- Remove impressions when set
- Inspect impressions for landmarks
- Perform otoscopy
- Put impressions in box
- End timer
- Administer questionnaires

- Introduction – “I will be using this camera to take some scans of your ear canals. I will place a headset on you and this probe will be inserted into your canal. You will be able to view the procedure on the TV in front of you. Due to the nature of this study, I am going to ask you to hold any questions until after the procedure is done, but do not hesitate to let me know if you are experiencing any discomfort throughout the procedure.”
- Otoscopy
- Start timer
- Sanitize [REDACTED] tip and headset
- Enter patient info
- Hair management
- Headset placement
- Perform scans bilaterally
- Inspect scans for landmarks
- Press power button on screen to save scans
- End timer
- Administer questionnaires

**IN THE EVENT THAT A CLINICIAN FEELS AS THOUGH THE IMPRESSION/SCAN IS UNSATISFACTORY TO SEND IN FOR A CUSTOM PRODUCT, THE PROCEDURE WILL BE REPEATED. THE TIMING OF ALL PROCEDURES WILL BE RECORDED ON THE TIMING**

SRF-371

SKP-371

Confidential and proprietary.  
This document and its contents are confidential and proprietary to Sonova and shall not be reproduced or otherwise disclosed to anyone other than Sonova employees without written authorization from Sonova.

This printout is an uncontrolled copy. The original is stored in the Document Management System.  
Template: TPL-368 [2]

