## Clinical Investigation Plan (CIP)

each methodology will be tested for normality using a Shapiro-Wilk test. If the data are normally distributed, additional analysis will proceed immediately. If data are not normally distributed, transformation(s) may be performed on the data, as appropriate, to achieve an approximately normal distribution of the response data for further analysis.

Data (raw or transformed, per above) will then be subjected to analysis via linear mixed effects modeling. The model will be constructed to regress (raw or transformed) procedure time on a dummy variable of methodology (fixed effect), with a random effect of audiologist. This model will allow the investigators to evaluate the relative difference in procedure time between the methodologies, while removing and separately evaluating the variance contributed by the audiologist undertaking the procedure.

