## Clinical Investigation Plan (CIP)

### 8.1.1 Specifications of source documents

Timing measures will be recorded for both procedures and any additional attempts. Data from questionnaires will be compiled, but not statistically analyzed. Other data includes source intake form and Noah packages containing tympanometry and reflex thresholds, RECD, and REUR data.

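### Section 7.4 deletes a participant when either time is missing, and the plan gives no time for a procedure that is never completed, so the primary result may cover only people in whom both methods worked

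*Combined protocol and SAP*

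**What the plan says.** Section 7.4 sets the rule for missing times: "Participants with missing procedure time data for either or both methodologies will be excluded from statistical analysis entirely". Deletion is by participant, so a valid time on the other method goes too. The same section says drop-outs are not replaced, whereas 6.1.6 and 6.3 allow rolling recruitment after attrition.

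On repeats, 6.4.1 says: "Timing will be recorded for all attempts, but only the time recorded for the final impressions will be used in the data analysis". Its timing details add that, when the clinician finds a scan or impression unsatisfactory, "THE PROCEDURE WILL BE REPEATED". Section 8.1.1 agrees: "Timing measures will be recorded for both procedures and any additional attempts". No limit on attempts is given.

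The timing details stop the clock only at the end of a finished procedure: after the impressions are boxed, or after the scans are inspected and saved.

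The primary model in 7.3.2 regresses "procedure time on a dummy variable of methodology (fixed effect), with a random effect of audiologist". It has no participant term. The dataset in 7.3.1 holds time, audiologist, participant, method and ordinal number, but no completion status or reason.

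The stated purpose in 5.1 is: "This information will allow us to find out whether this is a viable piece of equipment for Audiological Care clinics". Section 6.3 describes the sample thus: "Investigation population will contain a variety of external auditory canal sizes and shapes".

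**The concern.** Each participant has both methods in one appointment. A time can be absent for a reason unrelated to the method, such as a timer fault, or because one method was stopped. The documents foresee routes to the second kind: discomfort and skin irritation are listed in 14.2, withdrawal is immediate on request (6.3), and device deficiencies are collected (Section 14). Section 7.4 treats both kinds alike.

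A participant who cannot be scanned bears directly on whether the scanner suits clinics. Under 7.4 that participant may leave the primary comparison, and no planned table or analysis shows it by method. The reported difference would then apply to people in whom both methods worked, but be read as applying to clinic patients.

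**Working it through.** **Is there a figure to reproduce?** No. The plan gives no non-completion rate and no time for an incomplete procedure. The sample size of 30 cannot serve as a check: 7.1 says no sample size estimation was done, and no effect size, significance level or power is stated.

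**What the text allows.** Suppose a scan is abandoned. The defined end of timing is never reached, and there is no final scan whose time could be used. Staff can (i) leave the time missing, so 7.4 deletes the participant, or (ii) enter the last attempt's elapsed time. The plan does not choose.

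**Size when the cost of failure is counted.** Let D be the mean difference (scanner minus silicone) among completers, and let each of m failures cost E minutes more than D. The mean over all 30 is [(30 − m) × D + m × (D + E)] / 30 = D + m × E / 30. The completers' result therefore understates the all-participant difference by m × E / 30.

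If a scan abandoned after t minutes is followed by silicone, that person's extra time over silicone alone is t, so E = t − D. Section 6.2 gives about 15 min for each method. Taking D = 0 on that basis, E = 15 if the failed scan runs the full nominal time and E = 5 if it stops at 5 min. Both values of E, and m, are assumptions.

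| m of 30 | E = 5 min | E = 15 min |
|---|---|---|
| 1 | 0.17 | 0.5 |
| 3 | 0.5 | 1.5 |
| 5 | 0.83 | 2.5 |

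Silicone failures act in the opposite direction.

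**Size when only speed is at issue.** A narrower question is whether deletion distorts the time each method would have taken if completed. Assume normal times with SD 5 min per method (one reading of the synopsis, which is ambiguous), true difference 0, within-person correlation ρ, and that the slowest fraction f on the scanner fail. The bias is −(1 − ρ) × SD × φ(z) / (1 − f), where z is the upper-f normal quantile. At f = 10%, φ(z) = 0.1755 and 5 × 0.1755 / 0.9 = 0.97, giving:

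- ρ = 0: −0.97 min
- ρ = 0.5: −0.49 min
- ρ = 0.7: −0.29 min
- ρ = 1, or failure unrelated to speed: 0

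For ρ from 0.7 to 0, the bias is −0.12 to −0.38 min at f = 1/30 and −0.52 to −1.75 min at f = 20%.

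**Option (ii).** Suppose 10% of scans fail, unrelated to speed, and are entered at 5 min against a nominal 15. The shift is 0.10 × (5 − 15) = −1.0 min in the scanner's favour. Scored at 30 min (15 elapsed plus 15 for silicone) it is 0.10 × (30 − 15) = +1.5 min. The answer therefore depends on a choice the plan leaves open.

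**Would keeping the other method's time help?** Not under the 7.3.2 model as written. With no participant term, that model in effect compares two method means. Keeping everyone's silicone time leaves the silicone mean unshifted, while the scanner mean still shifts by −0.97 min at f = 10%. At ρ = 0.7 the bias is then −0.97 min, against −0.29 with pair deletion. A participant random effect lessens this but does not remove it, because missingness here depends on the unobserved time.

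**How likely is a case?** The chance of at least one in 30 is 1 − (1 − p)^30: 45% at p = 2%, 79% at 5% and 96% at 10%. These rates are also assumptions.

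**The case against.** A reader might infer that every failed scan disappears and that the failing method must then look faster. The documents do not support that. Attempts are timed and unsatisfactory ones repeated, so an unsatisfactory scan normally has a time and 7.4 need not apply. Deletion shifts the estimated speed only if failure goes with slowness on that method beyond the same person's slowness on the other.

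Other objections also stand:

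- The documents do not say that missing times arise mainly from failed procedures. Canals must be medically unremarkable and surgical ears are excluded, which may keep failures few.
- The synopsis figure of about 5 minutes describes variability. It is not a relevant difference against which to judge the bias.
- Non-completion is not wholly unrecorded. Repeat reasons go on the clinician questionnaire, adverse events and device deficiencies on the case report form, and attrition in a spreadsheet. Section 7.4 also calls for achieved power if the planned sample size is missed. One therefore cannot say that failures leave every reported count. But these are records; questionnaire data are not statistically analysed (7.3.3, 8.1.1), and no tabulation by method is planned.
- Counting a failed scan as scan plus silicone answers a different question from the time to complete one workflow. It belongs in a sensitivity analysis, and it cannot be computed for someone who leaves before the second method.
- The study is exploratory, with no effect size or margin (5.3).

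These points limit the strength and size of the concern. They do not supply the missing rule.

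**Conclusion.** The concern holds in conditional form. Section 7.4 deletes whole participants, and nothing defines the time for a procedure that is never completed. Depending on how staff fill that gap, the primary result either describes people in whom both methods worked, and may favour a method with procedure-related non-completions, or includes truncated times as if complete.

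The size is illustrative: 0.17 to 2.5 min for one to five failures in 30 with E from 5 to 15 min. On the speed-only view it is 0 to about 1 min at 10% non-completion with SD 5 min. Rates, E, SD and correlation are all assumed. The change is worth making because it affects what the study can say about viability in clinics and costs little.

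**What to change.** Amend 7.4 as follows.

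- **(a) Record.** Log each non-completed procedure with method, order, elapsed time and reason (procedure-related, device deficiency, or unrelated, such as a timer fault). Do not enter it as a completed time.
- **(b) Label and count.** Describe the primary result as time among participants who completed both methods. Beside it, report for each method the number completed out of the number started.
- **(c) One sensitivity analysis.** Count procedure-related non-completion as elapsed time plus that participant's time with the other method where available, or as the worst rank in a paired rank test. State in advance which.
- **(d) Model.** Do not keep the unpaired time of the completed method in the 7.3.2 model unless a participant random effect is added. Even then, treat it as no substitute for (b) and (c).
- **(e) Reconcile.** Bring 7.4 (no replacement of drop-outs) into line with 6.1.6 and 6.3 (rolling recruitment). If recruitment continues after attrition, the counts in (b) should still include everyone who started.

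The cost is some wording in 7.4, a reason field on the timing record, one extra analysis, and a completion caveat on the headline result. No extra visits are needed.

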Number of Participants with Rationale:	N = 30 (10 participants per researcher). Both conditions will be measured for each participant. This sample population will provide an adequately powered study under the assumption that time variance of each condition is within approximately 5 minutes.		

SRF-371

Confidential and proprietary.

This document and its contents are confidential and proprietary to Sonova and shall not be reproduced or otherwise disclosed to anyone other than Sonova employees without written authorization from Sonova.

This printout is an uncontrolled copy. The original is stored in the Document Management System  
Template: TPL-368 [2]

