#### 5.2 Primary and Secondary Objectives

The Primary objective is to identify any significant differences in the time required for a provider to complete the workflow of an [REDACTED] 3D ear scanner, compared to traditional silicone earmold impression procedures. The secondary objective is to identify any significant preferences for both providers and patients.

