#### 5.3 Scientific justification and clinical relevance for effect sizes, non-inferiority margins or equivalence limits

This is an exploratory trial, and as such, no specific effect size, non-inferiority margin, or equivalence limit is applicable.

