### 7.1 Determination of Sample Size

A priori sample size estimation was not performed for this investigation, as the investigation is exploratory and does not aim to confirm any effect with statistical significance and power.

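### Section 7.4 promises an achieved-power figure if fewer than 30 are analysed but fixes no effect, SD or alpha for it; report the difference with a 95% confidence interval instead (minor)

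*Combined protocol and SAP*

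**What the plan says.** Section 7.4 excludes any participant who lacks a procedure time for either method, says drop-outs are not replaced, and then adds: "Achieved statistical power will be calculated and documented if the planned sample size is not achieved". It does not say at which effect, SD, alpha or model the power is to be calculated.

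The other sections do not supply these inputs:

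- Section 5.3: "no specific effect size, non-inferiority margin, or equivalence limit is applicable".
- Section 7.1: "A priori sample size estimation was not performed for this investigation", because the study is exploratory and "does not aim to confirm any effect with statistical significance and power".
- Synopsis, number of participants: "N = 30 (10 participants per researcher). Both conditions will be measured for each participant". It continues: "This sample population will provide an adequately powered study under the assumption that time variance of each condition is within approximately 5 minutes". No target difference, power value or alpha accompanies this.
- Section 5.2: the primary objective is to "identify any significant differences in the time required for a provider" to complete each workflow. This implies a two-sided comparison but gives no level.

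Section 7.3.2 plans a linear mixed model with a fixed effect of methodology and a random effect of audiologist, on raw or transformed times. It says: "This model will allow the investigators to evaluate the relative difference in procedure time between the methodologies". Section 7 plans no confidence interval or other measure of precision.

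**The concern.** Power is a property of a design at a stated effect. Calculated after the trial, it is informative only if that effect was fixed beforehand, and here none was. Two routes remain. Power at the observed effect converts the p-value to another scale. Power at an effect picked after the results are known can be made large or small by the choice.

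The study is meant to inform whether the scanner is viable for the clinics. For that, readers need to know which differences in procedure time remain plausible and which are excluded. If the sample falls short and the time difference is not significant, an observed-effect power of about 0.5 or less follows from the p-value alone. It could then be offered as if it were separate evidence that the study was too small.

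**Working it through.** **1. Can the plan's own power statement be reproduced?** No. The synopsis gives N = 30 and a figure of about 5 minutes, but no difference to detect, power or alpha. The meaning of the 5 minutes is also open. For a paired t-test with n = 30 (two-sided 5%, assumed), the difference detectable with 80% power is 0.529 × SDd, where SDd is the SD of the within-participant difference and SDd = SD × √(2(1 − ρ)).

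- If 5 minutes is the SD per method: SDd is 7.07 min at ρ = 0 and 3.54 min at ρ = 0.75, so the detectable difference is 3.74 or 1.87 min.
- If 5 is a variance (SD 2.24 min): 1.67 min at ρ = 0 and 0.84 min at ρ = 0.75.

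The statement therefore fixes no effect at which power could later be recalculated.

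**2. Power at the observed effect.** Inputs: paired t-test, two-sided alpha 0.05 (assumed; the documents give none). Let t be the observed statistic for a given p and c = t(0.975, n − 1). Observed power = P(T > c) + P(T < −c), where T is noncentral t with n − 1 degrees of freedom and noncentrality t. For example, at n = 30 and p = 0.05, t = c = 2.045 and the power is 0.507.

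| p | n = 30 | n = 27 | n = 24 | n = 20 |
|---|---|---|---|---|
| 0.01 | 0.759 | 0.763 | 0.767 | 0.775 |
| 0.05 | 0.507 | 0.508 | 0.509 | 0.511 |
| 0.10 | 0.376 | 0.376 | 0.376 | 0.375 |
| 0.20 | 0.245 | 0.245 | 0.244 | 0.243 |
| 0.50 | 0.101 | 0.101 | 0.101 | 0.100 |

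Between n = 30 and n = 24, the figure at a given p moves by 0.002 or less for p of 0.05 and above, and by 0.008 at p = 0.01, where it goes up as participants are lost. SDd does not enter the formula. At n = 24 and p = 0.20 the observed power is 0.244 whether SDd is 2 min (95% interval −0.31 to 1.38 min) or 10 min (−1.53 to 6.92 min). Those two results would mean different things to a clinic.

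**3. What an interval shows.** Half-width = t(0.975, n − 1) × SDd / √n.

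| Analysed | Lost | Half-width (in SDd) | Ratio to n = 30 |
|---|---|---|---|
| 30 | 0 | 2.045/√30 = 0.373 | 1.000 |
| 29 | 1 | 2.048/√29 = 0.380 | 1.019 |
| 27 | 3 | 2.056/√27 = 0.396 | 1.059 |
| 24 | 6 | 2.069/√24 = 0.422 | 1.131 |

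With an assumed SDd of 5 min, the half-width is 1.87 min at n = 30 and 2.11 min at n = 24. Over SDd from 3 to 7.07 min, it is 1.12 to 2.64 min at n = 30 and 1.27 to 2.99 min at n = 24.

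**4. Link to the planned model.** These are paired t-test figures. For a t or Wald test of the methodology coefficient in the mixed model, observed power is likewise a function of that test's p-value, so the argument in step 2 carries over. The half-widths do not carry over: the planned model has no participant effect and may use transformed times.

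**The case against.** The strongest reply is that section 7.4 never says the observed effect will be used. The sponsor might intend to repeat the synopsis calculation at the number actually analysed, and power at a fixed effect does respond to drop-outs: an effect with 80% power at n = 30 has 75% at n = 27 and 70% at n = 24 (paired t, two-sided 5%). This stands as a correction to a stronger reading. A reader might infer that section 7.4 commits the sponsor to a figure that merely restates the p-value. The text does not say so; it leaves the inputs open. The reply does not rescue the sentence, because step 1 shows that the synopsis holds no effect to reuse.

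Three further limits also stand. The rule applies only on a shortfall, so with 30 complete participants nothing is calculated. A shortfall may be small or absent: each participant attends one appointment, and sections 6.1.6 and 6.3 allow rolling recruitment after attrition, although this conflicts with section 7.4. And section 7.4 gives a trigger but no purpose, so it cannot be faulted for failing at an aim it does not state.

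A reader might also infer that every significant result would look well powered. The figures contradict that: at p = 0.05 the observed power is only about 0.51.

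Finally, the study is exploratory and a fitted mixed model can readily supply an interval. Both are true. They make the change easy, but the plan does not commit to reporting one.

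**Conclusion.** The point holds as a minor one. The achieved-power rule has no defined inputs. It can be carried out only at the observed effect, where it repeats the p-value and is almost independent of the number lost, or at an effect chosen after the data. Neither shows which time differences the data exclude.

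The observed-power values rest on an assumed two-sided 5% level and a paired t-test. The widening of about 2%, 6% and 13% for 1, 3 and 6 lost illustrates the same test, not the planned model. The documents give no drop-out rate, so the 13% should not be read as an expected loss; it corresponds to 6 of 30, or 20%, missing.

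The sentence does not change the primary estimate, the test or the analysis set. It affects what is reported and how it is read when fewer than 30 are analysed.

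**What to change.** Delete the achieved-power sentence from section 7.4. In sections 7.3.2 and 7.4, state:

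*Whatever the number analysed, the methodology difference from the final primary model will be reported with its 95% confidence interval, back-transformed if times were transformed, and with the number of participants analysed out of 30. A non-significant result will not be read as equal procedure time.*

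If the sponsor prefers to keep a power figure, the effect, SD and alpha must be written into the plan before data collection. The synopsis statement on power should in any case be reconciled with section 7.1, and the no-replacement rule in section 7.4 with sections 6.1.6 and 6.3, since that rule decides whether a shortfall arises at all.

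The cost is a short edit in each of two sections. No extra data or participants are needed, and the interval comes from the model already planned.
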